## **11.7 STUDY FILES AND RETENTION OF RECORDS**

Copies of all study documents should be retained by the Investigator until at least two years after the last approval of a marketing application in an ICH region and until there are no pending or contemplated marketing applications in an ICH region or at least two years have elapsed since the formal discontinuation of clinical development of the investigational product, in accordance with 21 CFR 312.62. These documents should be retained for a longer period however, if required by regulatory requirements or by agreement with the Sponsor. It is the responsibility of the Sponsor to inform the Investigator/institution as to when these documents no longer need to be retained. The final database will be archived according to the regulatory requirements.

## **11.8 CASE REPORT FORMS**

Data for this protocol will be collected on to the source documents and later will be captured electronically in an Electronic Data Capture (EDC) system by the site coordinators. Source documents are original

records of clinical findings, observations, or other activities in a clinical trial necessary for the evaluation of the trial. Examples of source documents (electronic or hardcopy documents) include but are not limited to subject diaries, physician and/or patient completed questionnaires or scales, laboratory results, ECGs and reports. Designated study personnel will be provided unique usernames and passwords with specific access within the electronic data collection system based on their role. The EDC system contains an audit trail associated with each individual's unique password that will document date and time of data entry and revisions. All protocol-specified data is to be entered into the EDC system in a timely manner for review and audit by XBiotech. All data is to be entered such that it will allow accurate interpretation and tabulation. It is the Investigator's responsibility to ensure that all discontinued orders or changes in study or other medications entered into the database correspond to entries in the subject's medical records (i.e. source documents) and to acknowledge accurate completion of the eCRF.

## **11.9 DRUG ACCOUNTABILITY**

A Drug Dispensing Log must be kept current and should contain the following information:

- Initial inventory upon receipt of supplies at the study site
- Identification number of each subject to whom test drug was administered
- Date(s), quantities, lot numbers and calculations for all test drugs administered
- Final inventory (upon completion of the study)

This inventory must be available for inspection by the Clinical Research Associate. The Investigator (or pharmacist, as appropriate) must maintain records of the delivery of the study medication to the study site, the inventory at the site, the usage for each subject, and destruction. The inventory must be available for monitoring, auditing or inspection. A drug dispensing log must be kept current and should contain the following information:

- The subject identification number to whom the drug is dispensed
- The lot number of the drug dispensed
- The date(s) and the quantity of the drug dispensed to the subject

The sites will follow their internal SOPs for discarding the used (empty) syringes after the injection. The designated personnel at the sites will review drug accountability logs to account for administered syringes. Unused inventory by investigative sites at study completion should be returned to drug distributor for destruction per guidance provided in the study's pharmacy manual.

## **11.10 AUDITS AND INSPECTIONS**

Investigator sites, the study database and study documentation may be subject to quality assurance audits during the course of the study either by the Sponsor or their appointed representatives. In addition, regulatory bodies at their discretion may conduct inspections. The Investigator shall permit the authorized Sponsor, agents of the Sponsor, and regulatory agency employees to enter and inspect any site where the drug or records pertaining to the drug are held, and to inspect all records relating to an investigation, including subject records. The Sponsor will not, however, copy any source data from the patient's dossier. Completed eCRFs must be made available by the Investigator for review by the Sponsor, agents of the Sponsor, the CRA and the regulatory agencies. To ensure the accuracy of data submitted, it is mandatory that representatives of the Sponsor and of the regulatory agencies have direct access to source documents (e.g., subject medical records, charts, laboratory reports, etc.). Subject confidentiality will be protected at all times.

## **11.11 ACCESS TO INFORMATION FOR MONITORING**

The study will be conducted in compliance with Good Clinical Practice (GCP). Sponsor will arrange the clinical research associates (CRAs) to monitor the conduct of the clinical trial at the investigative sites. XBiotech ensures that appropriate monitoring procedures are performed before, during and after the study. All aspects of the study are reviewed with the investigator and the staff at a study initiation visit (SIV). Prior to enrolling subjects into the study, a XBiotech representative will review the protocol, eCRFs, procedures for obtaining informed consent, record keeping, and reporting of AEs/SAEs with the investigator and his/her staff. Monitoring will include on-site visits at regular intervals with the investigator and his/her staff as well as any appropriate communications by mail, email, facsimile, or telephone. During monitoring visits, the facilities, IP storage area and conditions, eCRFs, subject's source documents, and all other study documentation will be inspected/reviewed by the XBiotech representative. Accuracy and protocol compliance will be checked by performing source data verification that is a direct comparison of the entries made onto the eCRFs against the appropriate source documentation. Any resulting discrepancies or deviations from the protocol will be reviewed with the investigator and/or his/her staff. Any necessary corrections will be made directly to the eCRFs or via queries by the investigator and/or his/her staff. Monitoring procedures require that informed consents, adherence to study protocol and documentation of AEs and SAEs and their proper recording be verified. The CRA will make written reports to the Sponsor on each occasion when contact with the Investigator is made, regardless of whether it is by phone or in person.

## **11.12 STUDY DISCONTINUATION**

If the study is prematurely terminated or suspended, the Sponsor will promptly inform the Investigators/institutions and the regulatory authority(ies) of the termination or suspension and the reason(s) for the termination or suspension. The IRB/EC will also be promptly informed and provided with the reason(s) for the termination or suspension by the Sponsor or by the Investigator/institution, as specified by the applicable regulatory requirement(s).

## **COVID-19 APPENDIX**

### **GUIDANCE ON STUDY CONDUCT DURING THE COVID-19 PANDEMIC**

It is recognized that the Coronavirus Disease 2019 (COVID-19) pandemic may have an impact on the conduct of this clinical study due to, for example, self-isolation/quarantine by patients and study-site personnel; travel restrictions/limited access to public places, including hospitals; study site personnel being reassigned to critical tasks.

In alignment with recent health authority guidance, the sponsor is providing options for study-related patient management in the event of disruption to the conduct of the study. This guidance does not supersede any local or government guidelines or requirements or the clinical judgement of the investigator to protect the health and well-being of patients and site staff. If, at any time, a patient's safety is considered to be at unacceptable risk, drug product will be discontinued, and study follow-up will be conducted.

Scheduled visits that cannot be conducted in person at the study site will be performed to the extent possible remotely/virtually or delayed until such time that on-site visits can be resumed. At each contact, patients will be interviewed to collect safety data. Key efficacy endpoint assessments should be performed if required and as feasible. Patients will also be questioned regarding general health status to fulfill any physical examination requirement.

Every effort should be made to adhere to protocol-specified assessments for patients on drug product, including follow up. Modifications to protocol-required assessments may be permitted via COVID-19 Appendix after consultation between the patient and investigator, and with the agreement of the sponsor (see below).

The sponsor will continue to monitor the conduct and progress of the clinical study, and any changes will be communicated to the sites and to the health authorities according to local guidance. If a patient has tested positive for COVID 19, the investigator should contact the sponsor's responsible medical officer to discuss plans for drug product and follow-up. Modifications made to the study conduct as a result of the COVID-19 pandemic should be summarized in the clinical study report.

**ADDITIONAL ELEMENTS, WHERE APPLICABLE:**

- Certain protocol-mandated visits to the study site may not be possible during the COVID-19 outbreak. Therefore, temporary measures may be implemented if considered appropriate by the sponsor and investigator to maintain continuity of patient care and study integrity. Certain measures, such as those listed below, may be necessary and should be instituted in accordance with applicable (including local) laws, regulations, guidelines, and procedures:
  - remote (eg, by phone / telemedicine) or in-person, off-site (eg, in-home) interactions between site staff (or designees) and patients for study procedures e.g. those related to safety monitoring / efficacy evaluation / drug product storage and administration (including training where pertinent)
  - procurement of drug product by patients (or designee) or shipment of drug product from the study site directly to patients for at home administration (including the potential for self-administration of drug product)
  - laboratory assessments using a suitably accredited local laboratory; for selected measures (eg, urine pregnancy), home testing may be employed
  - other procedures, eg, imaging, may be conducted at an appropriate facility
- Missed assessments/visits will be captured in the case report form (CRF) for protocol deviations. Discontinuations of drug products and withdrawal from the study should be documented with the prefix “COVID-19-related” in the CRF.
  - other relevant study data elements impacted by the pandemic should also be documented / labeled as “COVID-19-related” in CRFs and / or other study systems, as directed by detailed sponsor guidance. These may include missed / delayed / modified study visits / assessments / dosing, and instances where temporary measures such as those above are implemented.
- The sponsor will evaluate the totality of impact of COVID-19 on collection of key study data and additional data analyses will be outlined in study SAP(s).
- Precaution: for those who may carry a higher risk for severe COVID-19 illness (eg, those aged over 65 years), follow guidance from local health authorities when weighing the potential benefits and risks during participation in the study.

**ABBREVIATIONS**

ADA	anti-drug antibody
AE	adverse event
ALT/SGPT	alanine aminotransferase
ALP	alkaline phosphate
ANCOVA	analysis of covariance
AST/SGOT	aspartate aminotransferase
ATC	anatomic and therapeutic Class
AUC	area under the curve
BMI	body mass index
BSA	body surface area
CI	confidence interval
CL	total systemic clearance
C max	maximum concentration
CRF	case report form
CSR	Clinical Study Report
CTCAE	Common Terminology Criteria for Adverse Events
CV	coefficient of variation
DLQI	Dermatology Life Quality Index
DMC	Data Monitoring Committee
DPS	Data Presentation Specifications
EASI	Eczema Area and Severity Index Score
ECG	Electrocardiogram
ELISA	Enzyme-linked immunosorbent assay
eCRF	electronic case report form
F (%)	absolute SC bioavailability
FAS	full analysis set
FDA	Food and Drug Administration
GISS	Global Individual Signs Score
HADS	Hospital Anxiety Depression Scale
ICH	International Conference on Harmonization
IGA	Investigator's Global Assessment
IQ	interquartile
IL-6	Interleukin-6
LLOQ	lower limit of quantification
LOCF	last observation carried forward
MedDRA	Medical Dictionary for Regulatory Activities
MRD	minimum required dilution
Nab	neutralizing antibodies
NRS	Numerical Rating Scale
PD	pharmacodynamic
PI	principal investigator
PK	pharmacokinetic(s)
POEM	Patient Oriented Eczema Measure
PP	per protocol
SCORAD	Severity Scoring of Atopic Dermatitis
SAE	serious adverse event
SAP	Statistical Analysis Plan
SD	standard deviation
SMQs	standardised MedDRA queries
TB	Tuberculosis
TEAE	treatment-emergent adverse event
US NCI	United States National Cancer Institute
WHO	World Health Organization
WHO-DD	World Health Organization Drug Dictionary

**Summary of Amendment 1**

This amendment is to add additional statistical method of Fisher's Exact test for the binary efficacy endpoints in case of rare events. Originally, the planned analysis for treatment comparison in binary response endpoints is to use a Cochran-Mantel-Haenszel test.

## 1. INTRODUCTION

This statistical analysis plan (SAP) contains definitions of analysis sets, derived variables, and statistical methods for the analysis of efficacy, safety, pharmacokinetics (PK), pharmacodynamics (PD), Immunogenicity and health-related quality of life in the JNJ77474462ADM2002(PT-046) study.

### 1.1. Trial Objectives

#### Primary Objective

The primary objective of this study is to evaluate the initial efficacy, safety of different dose regimens of bermekimab in adult participants with moderate to severe Atopic Dermatitis (AD).

#### Secondary Objectives

The secondary objectives of this study are:

- To evaluate the effect of bermekimab on the dermatologic health-related quality of life in adult participants with moderate to severe AD.
- To evaluate the pharmacokinetics (PK), immunogenicity, and pharmacodynamics (PD) of bermekimab therapy in adult participants with moderate to severe AD.

### 1.2. Trial Design

This is a phase II, randomized, double-blind, placebo-controlled study to further establish the efficacy, safety, PK, and explore dose effects for bermekimab monotherapy in adults with moderate to severe Atopic Dermatitis (AD). The participant population will comprise men and women who have had chronic atopic dermatitis present for at least 3 years. The study is approximately 40 weeks (30 day screening period, 32-week treatment period and a 4-week follow-up period) for all subjects.

A diagram of the study design ([Figure 1](#)) is provided below, approximately 90 patients who meet the eligibility criteria at screening will be randomized in a 1:1:1 ratio to one of two active treatment arms or placebo:

- Arm 1: 400 mg loading dose of bermekimab (2mL SC injection containing 400 mg of bermekimab and one 2mL SC injection of placebo) at Week 0 followed by weekly (qw) subcutaneous (SC) injections of 400 mg bermekimab through Week 31
- Arm 2: 800 mg loading dose of bermekimab (2 x 400 mg SC injections) at Week 0 followed by subcutaneous (SC) injections of 400 mg bermekimab every other week (q2w) alternating with matching placebo q2w through Week 31.

- Arm 3: 4mL loading dose of placebo (2 x 2mL SC injections) at Week 0 followed by weekly placebo injections from Week 1 through Week 15. Patients in Arm 3 will begin to receive weekly (qw) blinded subcutaneous (SC) injections of 400 mg bermekimab beginning at Week 16 through Week 31.

Patients will be monitored at a follow up visit (week 36) for safety and clinical assessments after completing the 32 week treatment period.

Efficacy assessments include Eczema Area and Severity Index Score (EASI) score, Itch Numerical Rating Scale (NRS), Pain NRS, Severity Scoring of Atopic Dermatitis (SCORAD), Patient Oriented Eczema Measure (POEM), Global Individual Signs Score (GISS), Dermatology Life Quality Index (DLQI), Hospital Anxiety Depression Scale (HADS), Body Surface Area (BSA) and Investigator's Global Assessment (IGA) will be performed according to the Study Calendars (Section 5.2 of the protocol).

Blood samples will be collected for laboratory testing including chemistry, hematology, inflammation markers, bermekimab concentration (PK), PD marker(s), and anti-drug antibody (ADA).

**Figure 1: Study Flow Diagram of JNJ77474462ADM2002**

	Screening	Treatment Period			Follow-up
		Baseline	Weekly Dosing	Endpoint Assessment	
Visit (V)		V1	V2 to V32	V33	V34
Week (W)	D -30 to -1	W0	W1 to W31	W32	W36
Day (D)		D0	D7 to D217	D224	D252

After completion of the 36-week study period, data will be locked and analysed for safety and efficacy. In addition to the analyses that will be performed following the formal Week 36 database lock at the end of the study, an additional database lock will be performed at Week 16 and the unblinded efficacy data analyses will be conducted to help plan potential future development activities.

### 1.3. Statistical Hypotheses for Trial Objectives

The primary hypothesis is that bermekimab treatment is superior to placebo as assessed by the proportion of participants achieving Eczema Area and Severity Index-75 (EASI-75) ( $\geq 75\%$  improvement from baseline in EASI score) at Week 16.

## 1.4. Sample Size Justification

The primary efficacy endpoint is percentage of patients with Eczema Area and Severity Index-75 (EASI-75) ( $\geq 75\%$  improvement from baseline) at Week 16. The sample size is calculated for the bermekimab weekly injection group (Arm 1) versus placebo group (Arm 3) comparison.

Assuming EASI-75 is achieved in 60% of intent-to treat (ITT) patients treated in the bermekimab weekly injection group (Arm 1) versus 20% in placebo treated patients (Arm 3), then, for a randomization ratio of 1:1:1, a sample size of 69 patients (23 in each treatment group) is required for approximately 80% power at a 2-sided 0.05 significance level using Pearson chi-square test. In order to account for possible dropouts and to provide adequate safety data, approximately 90 patients will be randomized and treated.

## 1.5. Randomization and Blinding

### 1.5.1. Procedures for Randomization and Stratification

A centralized block randomization schedule with a 1:1:1 allocation ratio will be utilized using an electronic randomization system. Patients will be randomly assigned to either the bermekimab weekly injection group (Arm 1), the bermekimab every other week injection group (Arm 2), or the placebo group (Arm 3). The randomization schedule will be stratified by baseline EASI severity (less severe [EASI <28] or more severe [EASI  $\geq 28$ ]).

### 1.5.2. Maintenance of Blind

The study blind will be maintained for the duration of the study, until after the Final (Week 36) DBL.

In order to maintain blinding, all patients will receive two injections at Week 0, followed by weekly injections from Week 1 to 31. Additionally, to ensure that no unintentional unblinding occurs during study drug administration, a qualified individual will be designated at each study site to perform all preparation and injection of the investigational product. The designated injector should have no other contact with the participant during the study, should not discuss the participant's treatment with the participant, participant's caregiver, or other site personnel at any time, and will not be permitted to review the participant's medical records, questionnaires, or the electronic CRF prior to each injection. The designated injector should be documented in the source documents at each visit.

The investigator will not be provided with randomization codes. The codes will be maintained within the Electronic Data Capture (EDC) system, which has the functionality to allow the investigator to break the blind for an individual participant.

Data that may potentially unblind the intervention assignment (ie, study intervention serum concentrations, anti-bermekimab antibodies, and intervention allocation) will be handled with special care to ensure that the integrity of the blind is maintained and the potential for bias is minimized. This can include making special provisions, such as segregating the data in question

from view by the investigators, clinical team, or others as appropriate until the time of DBL and unblinding.

Under normal circumstances, the blind should not be broken until all participants have completed the study and the database is finalized. However, a number of prospectively identified Sponsor individuals will be unblinded at the Week 16 DBL. Identification of sponsor personnel who will have access to the unblinded data at subject-level and who will have access to the unblinded data at group-level will be documented prior to unblinding at the Week 16 DBL. All site personnel and participants will remain blinded to the treatment assignments until the last participant completes Week 36 evaluations and the database has been locked.

In the event of an emergency that would require the investigator to be aware of the treatment allocation prior to the end of the trial, the investigator can obtain this information, on a per subject basis, after consultation with the Sponsor's Medical Monitor, if possible. Every effort should be made to consult with the Medical Monitor prior to emergency unblinding. Events that qualify as emergencies are as follows:

- A grade 3 or greater AE which are “probably or definitely” related to study drug, and only if treatment assignment information is essential for the management of the event. This type of reaction would require that the patient receives no further doses and is followed until the resolution of the toxicity.
- Any suspected, unexpected, serious adverse reaction (SUSAR)
- Pregnancy

The investigator may, in an emergency, determine the identity of the intervention through the EDC system. While the responsibility to break the intervention code in emergency situations resides solely with the investigator, it is recommended that the investigator contact the sponsor or its designee if possible, to discuss the particular situation, before breaking the blind. Telephone contact with the sponsor or its designee will be available 24 hours per day, 7 days per week. In the event the blind is broken, the sponsor must be informed as soon as possible. The date and reason for unblinding must be documented in the appropriate section of the eCRF, and in the source document.

Participants who have had their intervention assignment unblinded by the investigator will not be eligible to receive further study intervention but should continue to complete evaluations specified in the Study Calendars (Section 5.2 of the protocol).

## **2. GENERAL ANALYSIS DEFINITIONS**

This analysis plan provides the general analysis definitions and describes the planned subject information, efficacy, safety, pharmacokinetics, and antibody analyses for the two planned DBLs.

### **2.1. Imputation Rules for Partial or Missing AE Dates**

Partial AE onset dates will be imputed as follows:

- If the onset date of an adverse event is missing day only, it will be set to:
  - First day of the month that the AE occurred, if month/year of the onset of AE is different than the month/year of the study agent start
  - The day of study agent start, if the month/year of the onset of AE is the same as month/year of the study agent start date and month/year of the AE resolution date is different
  - The day of study agent start or day of AE resolution date, whichever is the earliest, if month/year of the onset of AE and month/year of the study agent start date and month/year of the AE resolution date are same
- If the onset date of an adverse event is missing both day and month, it will be set to the earliest of:
  - January 1 of the year of onset, as long as this date is on or after the study agent start date
  - Month and day of the study agent start date, if this date is in the same year that the AE occurred
  - Last day of the year if the year of the AE onset is prior to the year of the study agent start date,
  - The AE resolution date.
- Completely missing onset dates will not be imputed.

Partial AE resolution dates not marked as ongoing will be imputed as follows:

- If the resolution date of an adverse event is missing day only, it will be set to the earliest of the last day of the month of occurrence of resolution or the date of death, if the death occurred in that month.
- If the resolution date of an adverse event is missing both day and month, it will be set to the earliest of December 31 of the year or the day and month of the date of death, if the death occurred in that year.
- Completely missing resolution dates will not be imputed.

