#### **2.4.2. Safety Analysis Set**

The safety analysis set includes all randomized participants who received at least 1 dose of study agent, i.e., the treated population.

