### **Summaries through Week 36**

Safety data through Week 36 will be summarized by treatment groups including

1. Placebo → bermekimab qw
2. Bermekimab q2w
3. Bermekimab qw
4. Combined Bermekimab

This allows safety comparisons between each bermekimab regimen through Week 36 based on the similar follow-up time in each group.

The list of actual treatment groups for safety analyses and inclusions of participants and safety events/measurements in each group are defined as follows:

1. **Placebo:** all participants who were randomized to placebo and received treatment with placebo only or received treatment with placebo prior to receiving treatment with bermekimab. For participants who started treatment with placebo but later received bermekimab, the safety events/measurements on and after the first dose of bermekimab will be excluded from this group. Only the safety events/measurements that occurred while the participants had been receiving placebo only will be included in this group.
2. **Placebo → bermekimab 400 mg qw:** all participants who were randomized to placebo started treatment with placebo only and later received treatment with bermekimab qw. Only the safety events/measurements from these participants that occurred on and after their first administration of bermekimab will be included in this group.
3. **Bermekimab 400 mg qw:** all participants who were randomized to bermekimab qw and received bermekimab qw. All the safety events/measurements from these participants that occurred on and after their first administration of bermekimab will be included in this group.
4. **Bermekimab 400 mg q2w:** all participants who were randomized to bermekimab q2w and received bermekimab q2w. All the safety events/measurements from these participants that occurred on and after their first administration of bermekimab will be included in this group.

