### 6.1. Adverse Events

The verbatim terms used in the CRF by investigators to identify adverse events will be coded using the Medical Dictionary for Regulatory Activities (MedDRA). Any AE starting at or after the initial administration of study agent through the end of the trial is considered as treatment emergent. If the event occurs on the day of the initial administration of study agent, and either event time or time of administration are missing, then the event will be assumed to be treatment emergent. If the event date is recorded as partial or completely missing, then the event will be considered as treatment emergent unless it is known to be prior to the first administration of study agent based on partial onset date or resolution date. All reported treatment-emergent adverse events will be included in the analysis.

The following analyses will be used to assess the safety of participants in the study:

- The incidence and type of AEs.
- The incidence and type of SAEs.
- AEs of severe intensity
- AEs leading to discontinuation of study
- The incidence and type of reasonably related AEs.

These summary tables will provide the count and percentage of participants with 1 or more of the specified AEs by treatment group. In addition to the summary tables, listings will be provided for participants who:

- Had SAEs
- Had AEs leading to discontinuation of study
- Had AEs of severe or life threatening, or fatal based on CTCAE (grade $\geq$ 3) intensity
- Had anaphylactic or serum sickness-like reactions.

Since safety should be assessed relative to exposure and follow-up, most AE summary tables will include average weeks of follow-up and average number of study agent administrations, and injections for each treatment group.

In addition, a participant who had injection site reaction(s) in 30 minutes (+/- 10) post injection at Weeks 0, 1, and 2 were recorded in eCRF. The incidence of injection-site reaction during this time frame will be summarized.

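### An Arm 3 adverse event whose incomplete onset date straddles the Week 16 switch is always dated to the placebo side, because the SAP's imputation rules ignore the first bermekimab dose

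*SAP*

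**What the plan says.** **Date rules (SAP 2.1).** Each partial-onset rule uses the start of study agent, the calendar month or year, and the resolution date.

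- Day missing, month different from the start month: "First day of the month that the AE occurred, if month/year of the onset of AE is different than the month/year of the study" (cut short).
- Day missing, all in the start month: "The day of study agent start or day of AE resolution date, whichever is the earliest".
- Day and month missing: the earliest of several candidates, including "January 1 of the year of onset, as long as this date is on or after the study agent start date" and "Month and day of the study agent start date, if this date is in the same year that the AE occurred".
- Nothing known: "Completely missing onset dates will not be imputed".

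Study agent includes placebo. SAP 2.4.2 says "The safety analysis set includes all randomized participants who received at least 1 dose of study agent", whereas the PK set in SAP 2.4.3 is defined by a dose of bermekimab.

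**Column rules (SAP 6, Summaries through Week 36).** Arm 3 events on or after the first bermekimab dose are taken out of the placebo group. For the placebo-to-bermekimab group, "Only the safety events/measurements from these participants that occurred on and after their first administration of bermekimab will be included in this group".

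**Treatment-emergent rule (SAP 6.1).** "If the event date is recorded as partial or completely missing, then the event will be considered as treatment emergent", unless it is known to precede the first study agent dose. This settles whether an event counts, not which Arm 3 column receives it.

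**The concern.** Two sections use two different reference dates for the same patients. Dating an uncertain onset as early as possible is cautious in Arms 1 and 2, where any post-baseline date still counts under bermekimab. In Arm 3 the same habit carries an event back across a treatment change. An event that may have begun on bermekimab is credited to placebo and dropped from the summary of first bermekimab exposure.

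The arm is small. About 90 patients randomised 1:1:1 gives about 30 in Arm 3, so one patient in the wrong column is 1/30, or about 3 percentage points. The injection-site-reaction summary in SAP 6.1 covers only Weeks 0, 1 and 2. Arm 3 reactions to the first bermekimab doses therefore reach the tables only through the column assignment of adverse events.

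**Working it through.** The plan states no figure here, so there is none to reproduce. The check applies the SAP 2.1 rules as written and then the SAP 6 column rule.

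**Inputs from the documents.** The switch is at Day 112 with a window of ±3 days (protocol 5.2, Visit 17). Adverse events are followed to Week 36, Day 252 (protocol 7 and the study calendar). Post-switch onsets therefore fall on Days 112 to 252, which is 141 days.

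**Assumptions.** First-dose dates cover every day of four calendar years (1,461 dates). Onset is uniform over Days 0 to 252. Event durations are 0, 3, 10 or 40 days, or ongoing, in equal shares. An ongoing event in the start month is set to the start day.

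**Column rule.** Imputed onset before the first bermekimab date goes to placebo; on or after it goes to placebo-to-bermekimab.

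**One example.** First dose 1 October 2020; switch 1 October + 112 days = 21 January 2021.

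| True onset | Day missing | Only year known |
|---|---|---|
| 29 Jan 2021 | 1 Jan 2021: placebo | 1 Jan 2021: placebo |
| 5 Feb 2021 | 1 Feb 2021: bermekimab | 1 Jan 2021: placebo |

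**Direction.** The imputed onset was never later than the true onset. Of 818,160 placebo-period cases, 0 moved to the bermekimab column. The count is also 0 with the switch at Day 109 or Day 115.

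**Extent, day missing.** Only onsets in the calendar month of the switch can move, and none do if the switch is on the 1st. In a month of L days with the switch on day k, L − k + 1 post-switch days are exposed, or 0 if k = 1. The average over k is (L − 1)/2, about 14.7 days over the calendar. Then 14.7/141 = 10.4%.

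- The enumeration agrees: 107,600/1,030,005 = 10.4%.
- Across the ±3 day window the share is 10.2% to 10.7%. By first-dose date it runs from 0% to 21%.
- Onsets in months after the switch month: 0 of 915,100 moved.

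**Extent, only the year known.** The share is 829,785/1,030,005 = 81%, and 0% to 100% by first-dose date. These onsets move when the first dose is in the onset year, or when the switch falls after 1 January of that year. They do not move when 1 January of the onset year is on or after the switch.

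**Nothing known.** The onset is not imputed, so it is not moved. It is also not assigned to a column.

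**The case against.** The best case against acting is that few events are touched. Patients attend weekly with adverse events reviewed at each visit, and the protocol adds a check 30 minutes after injection at Weeks 16, 17 and 18. An event reported that way will seldom lack its day and hardly ever its month, so the year-only case is close to theoretical. The percentages above apply only to events that already have a partial date. SAP 6 plans no formal safety comparison, and serious events, events leading to discontinuation and events of grade 3 or higher are listed by participant. All of this stands, and it limits the weight of the point.

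Two stronger readings are tempting, and the documents do not support them.

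- **Any post-switch event in Arm 3 with an incomplete onset goes to placebo.** It does not. With the day missing, a later month stays under bermekimab. A year-only onset stays there if 1 January of that year is on or after the switch. A completely missing onset is unassigned, not moved, and a resolution date before the switch would show that it belongs to placebo.
- **The rule makes bermekimab look safer in the placebo-controlled comparison.** The SAP does not say whether the through-Week-16 cut uses imputed onset. If it does, Arm 1 and Arm 2 events just after Week 16 are pulled back before the cut in the same way, so their columns gain events too. What is specific to Arm 3 is the change of treatment column, which bears mainly on the uncontrolled placebo-to-bermekimab summary.

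The objection does not remove the inconsistency. For a straddling date, the written rules give a definite answer that favours bermekimab in Arm 3 each time.

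**Conclusion.** The point holds for straddling dates. These are onsets with the day missing in the month of the switch, or with only a year known that contains on-study dates on both sides of it. Such events always go to placebo, and nothing moves the other way. Completely missing onsets have no Arm 3 column rule.

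Under uniform start and onset dates, about 10% of post-switch events with the day missing would move. The absolute number cannot be estimated, because the documents do not give the share of partial dates; it is probably small. This is a cheap improvement to the safety tables and does not touch the efficacy analysis.

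**What to change.** Add to SAP 2.1, for participants randomised to placebo who received bermekimab:

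1. Suppose the known part of the onset date fits onset both before and on or after the first bermekimab dose: same month and year with the day missing, or same year with day and month missing. If the event did not resolve before that dose, set onset to the date of that dose.
2. If the known month or year lies wholly before or wholly after the switch, or the event resolved before it, keep the existing rules. This limit matters: a rule triggered whenever post-switch onset is possible would also overwrite a known later month.
3. Place an event with a completely missing onset in the placebo-to-bermekimab column, unless its resolution date precedes the first bermekimab dose.
4. List all events affected.

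**Cost.** A few sentences and one programming rule, with no new data. Applied to the same enumeration, the share of post-switch events moved back falls from 10.4% to 0% with the day missing.

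The error is reversed, not removed. Some true placebo-period onsets move to bermekimab: 59,105/818,160 = 7.2% of those with the day missing under the assumed durations. For events that are all ongoing, the share is 13% with the day missing and 85% with only the year known. That is the conservative direction for safety, and the listing lets a reader see each case.
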